### **Inclusion criteria**

Patient should fulfill all this characteristics to be included:

1-age more than 12 years old.

2-weight not less than 40 kg.

3-Moderate, sever or critical COVID-19 disease as defined by WHO.

4-PCR- confirmed patients to be Positive before inclusion.

### **Exclusion criteria**

Patient should not have any of the following to be included:

1-history of hypersensitivity or infusion related reactions after administration of monoclonal antibodies.

2-prior use of standard antiviral therapy (remedsvir or favipravir).

3-Current use of controversial antiviral therapy (hydroxychloroquine, ivermectin, nitazoxanide, oseltemavir, acyclovir, ribavirine, lopinavir/rotavirus, sofosbuvir, dectasevir, semipiravir, azithromycin).

4-patients expected to die within 48 hours.

## **Interventions:**

Population included in this study will be assigned into 3 groups with 1:2:2 ratios to receive either antibodies cocktail or standard antiviral therapy (remdesvir, favipravir) as shown in table2 and figures 2 & 3.

Group A patients will receive REGN3048-3051(Antibodies cocktail (casirivimab and imdevimab) ) in low-dose regimen 1.2 gm (1200 mg of combined antibodies) diluted in 250 ml 0.9% sodium chloride solution as single I.V infusion over 30-60 minutes.

Group B patients will receive Remdesivir :

Day1 (loading dose): 200 mg (two 100mg vials) diluted in 500ml 0.9% sodium chloride solution infused I.V over 60 minutes

Day 2-5 or Day 2-10 (maintenance dose): 100 mg (one 100mg vial) in 250 ml 0.9% sodium chloride solution infused I.V over 30 minutes

Group C patients will receive Favipravir :

[figure not shown]
Day 1 (loading dose): 1600 mg (8 tablets) or 1800 mg (9 tablets) orally or in Ryle tube / 12 hours

Day 2-5 or day 2-10 (maintenance dose): 600 mg (3 tablets) or 800 mg (4 tablets) orally or in Ryle tube / 12 hours

[figure not shown]
Patients will be received standard of care by Physicians, Clinical pharmacist , Nurses and as guided by Egyptian COVID-19 treatment protocol.

**Table 2 : The three intervention groups of the study**

		Frequency	Percent	Valid Percent	Cumulative Percent
Valid	A	53	20.0	20.0	20.0
	B	106	40.0	40.0	60.0
	C	106	40.0	40.0	100.0
	Total	265	100.0	100.0	

**Figure 2: Assignment of the included COVID cases at their groups.**

**Figure 3: Frequency of interventions in included patients**

## **Method:**

The type of this study is single blind non-RCT and is considered a Phase IV Clinical trial (post-marketing study) to report efficacy and safety of new medicine.

We use PubMed search tool to find clinical studies that performed to test efficacy and safety of developed immunotherapy in treatment of COVID-19 with about 4,000 results with focusing on antibodies developed as antiviral against COVID-19 obtaining only 70 results from which REGN-COV2, a Neutralizing Antibody Cocktail is selected with its only one clinical study up to now (REGN-COV2, a Neutralizing Antibody Cocktail, in Outpatients with Covid-19) which is published in New England Journal of Medicine on January 21, 2021.

Another resource used to obtain data is Fact Sheet for Health Care Providers-EUA OF casirivimab and imdevimab which provides clinical data about the use of this antibodies cocktail. Endnote citation software is used for citation of references.

## **Outcomes:**

Parameters that will be assessed during hospitalization at day 0(baseline), day 3, 7, 14, 28 include:

- C-reactive protein (CRP)
- ferritin
- lactate dehydrogenase (LDH)
- D-dimer
- serum creatinine(S.Cr) and estimated creatinine clearance(CrCl)
- alanine aminotransferase (ALT), aspartate aminotransferase (AST), albumin, bilirubin

Clinical outcomes measured before & during intervention

1) Primary outcomes

- 1- 28-days mortality rate (efficacy).
- 2-PCR test results at end of hospital visit (efficacy).
- 3-precentage of patients who developed infusion related or hypersensitivity reactions during and after the end of drug infusion and reporting of any Serious and unexpected adverse events may occur that have not been previously reported with REGEN-COV use that may cause drug discontinuation (Safety).

2) Secondary outcomes

- 1-Need for invasive mechanical ventilation.
- 2- Invasive mechanical ventilation and oxygen support duration (days).
- 3- Time to clinical improvement (defined as 2 points reduction in the WHO disease ordinal progression scale(11&12) or discharge, whatever happens first)
- 4- ICU and hospitalization length of stay (days).
- 5- SOFA score(13) on day 0,3,7,14, and 28.
- 6- COVID19 WHO disease progression score(11&12) from day 0 to day 28.
- 7- Inflammatory markers including CRP, ferritin, LDH
- 8- liver and kidney functions

In addition to clinical outcomes measured before and during intervention, Vital signs, glasgow coma score (GCS),complete blood count (CBC), artierial blood gas (ABG) and prothrombin time (PT) is recorded at day0.

Patients' charactrestics(age,gender) and relevant medical and medication history and current COVID-19 treatment drugs will be recorded on admission

Duration of research will be about 6 months from Novmber 2021 to March 2022

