## **Aim of the study:**

1-To evaluate the efficacy of antibodies cocktail (casirivimab and imdevimab) compared to standard antiviral therapy in reducing 28-day mortality in hospitalized patients with moderate, severe or critical COVID19

2-To evaluate safety of antibodies cocktail (casirivimab and imdevimab) compared to standard antiviral therapy by monitoring of hypersensitivity and infusion related reactions or other significant adverse effects

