## **Statistical Analysis Plan (SAP):**

Intention-to-treat strategy will be used in this study. Intention-to-treat strategy will be used in this study. Statistical analysis will be achieved with SPSS, version 26.

Categorical variables will be presented as proportion and percent. Continuous variables will be presented as mean (standard deviation) for parametric data or as a median (25th-75th percentile) for non-parametric data.

Regarding baseline characteristics, Kruskal-Wallis or ANOVA test (depending on type of data and the continuous data distribution (normal or not)) will be used to compare these characteristics between the study groups. We will report the P-value for our statistical tests with level of statistical significance will be P-value  $\leq 0.05$ .

In case of existing differences in some baseline characteristics, logistic regression will be performed. This allows studying the effect of these variables on the primary outcomes of the study to exclude the effect of these confounding variables and to ensure the effect on the outcomes is due to interventions.

Regarding the outcomes, we will compare the 28-day all-cause mortality rate, result of PCR test at hospital discharge and incidence of infusion related or hypersensitivity reactions during and after the end of drug infusion (primary outcome) using the Kruskal-Wallis test with reporting the P-value.

While the secondary outcomes (hospital stay duration, icu stay duration and others) are compared using Kruskal-Wallis or ANOVA test depending on type of data and the distribution of data (normal or not)

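### Primary outcome 3 ties safety reactions to a drug infusion, but group C takes tablets: the single Kruskal-Wallis P-value can reflect route alone, and no interval comparing the cocktail with either standard antiviral is planned

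*Combined protocol and SAP*

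**What the plan says.** **Outcome.** In the Outcomes section, primary outcome 3 is the "precentage of patients who developed infusion related or hypersensitivity reactions during and after the end of drug infusion", together with reporting of serious unexpected events.

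**Test.** The Statistical Analysis Plan repeats the definition and says the trial will compare the "incidence of infusion related or hypersensitivity reactions during and after the end of drug infusion (primary outcome) using the Kruskal-Wallis test", reporting the P-value. It names no groups, pairwise contrast, risk difference or interval for this outcome.

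**Other SAP provisions that bear on it.** "Categorical variables will be presented as proportion and percent". Also: "In case of existing differences in some baseline characteristics, logistic regression will be performed".

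**Routes (Interventions section).**
- Group A, the cocktail: given "as single I.V infusion over 30-60 minutes".
- Group B, remdesivir: an infused loading dose on day 1, then "Day 2-5 or Day 2-10 (maintenance dose): 100 mg (one 100mg vial", also infused.
- Group C, favipiravir: a day-1 loading dose of "1600 mg (8 tablets) or 1800 mg (9 tablets) orally or in Ryle tube", with maintenance by the same routes. No dummy infusion is described.

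**Aim.** Aim 2 is to evaluate the safety of the cocktail "compared to standard antiviral therapy by monitoring of hypersensitivity and infusion related reactions or other significant adverse effects". The Interventions section identifies the standard antivirals as remdesivir and favipiravir.

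**The concern.** The outcome joins two kinds of reaction and places both in time by reference to an infusion. One of the three groups has no infusion. For that group the infusion-related part is zero by construction. The hypersensitivity part is possible, but the plan does not say when observation starts. Staff must either leave out hypersensitivity in group C or choose a starting point themselves.

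The comparison is one overall test. Such a test asks whether any group differs from any other, and here at least one difference may come from route. At stake is what the primary safety result can say: the report could state a significant difference in reactions while the cocktail and remdesivir behave identically. A reader could then take the P-value as evidence about the cocktail's tolerability.

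**Working it through.** **Inputs.** Group sizes are A 53, B 106, C 106, total 265 (Table 2 and Sample Size). The Population section gives a different allocation ratio; that is a separate matter. The significance level is 0.05 (SAP). The documents give no expected reaction rate for any group, so every rate below is an assumption. The only stated sample-size figure, 246, concerns 28-day mortality. There is no planned figure for the safety outcome to reproduce. That the test covers all three groups is inferred, because no other comparison is given.

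**Infusions per patient.** A: 1. B: day 1 plus days 2-5 = 1 + 4 = 5, or day 1 plus days 2-10 = 1 + 9 = 10. C: 0.

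**Test statistic.** For yes/no data, Kruskal-Wallis with tie correction is H = [(N-1)/N] × Pearson chi-square, on 2 degrees of freedom for three groups.

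**Worked example: 3/53, 6/106, 0/106.**
1. Overall rate = 9/265 = 0.0340. Expected events are 1.8, 3.6 and 3.6.
2. Sum of (observed - expected)²/expected = 1.44/1.8 + 5.76/3.6 + 12.96/3.6 = 0.8 + 1.6 + 3.6 = 6.0.
3. Pearson chi-square = 6.0/(1 - 0.0340) = 6.21. H = 6.21 × 264/265 = 6.19.
4. P = exp(-6.19/2) = 0.045.
5. A versus B: 3/53 = 6/106 = 5.7%. Difference 0, Fisher P = 1.0, Newcombe 95% CI -7.2 to +10.2 points.

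These counts lie just past the threshold. One event fewer in B (3, 5, 0) gives P = 0.061, and 2, 4, 0 gives P = 0.13.

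**How often this would happen.** Exact binomial enumeration at 53/106/106, with the same true rate in A and B:

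| Assumed rate in A and B | C = 0 | C = 1% | C = 2% |
|---|---|---|---|
| 1% | 5.7% | 2.8% | 5.1% |
| 2% | 15.5% | 7.0% | 4.2% |
| 4% | 42.4% | 21.1% | 10.8% |
| 8% | 93.6% | 69.7% | 48.3% |

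Entries are the probability that the three-group test gives P ≤ 0.05. Where all three rates are equal (1%/1%/1% and 2%/2%/2%), the entry is the ordinary null rejection rate. The C = 1% and C = 2% columns allow for hypersensitivity recorded in group C.

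**Number of infusions.** A and B also differ in exposure. At an assumed 1% risk per infusion, taken as independent, the per-patient risk is 1% in A. In B it is 1 - 0.99^5 = 4.9% or 1 - 0.99^10 = 9.6%. A per-patient comparison of A with B therefore compares whole treatment courses and should say so.

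**What A versus B alone can show.** With 53 + 106 = 159 patients, two-sided Fisher power is 0.57 for 10% v 2%, 0.19 for 10% v 5% and 0.78 for 20% v 5% (assumed rates).

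**The case against.** **A lower rate in C is a true difference, so rejecting is correct.** This stands. A reader might infer from the table that the planned test has an inflated false-positive rate. It does not: when all three groups share a rate, it rejects in about 3% to 5% of trials. The larger figures are power against a route difference. The criticism concerns what the P-value can be taken to mean.

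**An overall test without contrasts is a general feature of this SAP.** Also true: mortality and PCR result are handled the same way. What is particular to safety is that the definition itself makes one group's infusion reactions impossible and leaves its hypersensitivity without a starting point.

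**The window is loose in every group.** It has no stated end in A or B either, and on an ordinary reading a hypersensitivity reaction in C could still be counted. This stands; only the missing start is peculiar to C.

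**Percentages will be shown.** A reader might infer that the plan yields no estimate at all. That goes too far: the outcome is a percentage, and if it is tabulated by group, a crude A-B difference can be read off and a zero in C would be visible. The planned inference is still a P-value alone, with no named contrast and no interval.

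**Logistic regression could supply contrasts.** It is conditional on baseline differences, is described as studying the effect of the baseline variables, and names no group contrast.

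**The aim is not only A versus B.** Correct. Aim 2 covers both standard antivirals, so the A-C contrast is missing as well.

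**Conclusion.** The point holds on the text, with high confidence. The outcome is anchored to an infusion that group C never receives, and its test does not show how the cocktail compares with either standard antiviral.

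The numerical size is uncertain because the documents state no reaction rates. If A and B share a rate of about 1% or below and C has none, the effect is small. At 4% to 8% a significant result becomes common (42.4% to 93.6%) although A and B are equal. It is less frequent if C records some hypersensitivity. The example counts show that the outcome is possible, not that it is likely.

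The documents do not support a claim that the test is invalid or that the efficacy conclusion is affected. The plan should be changed, and this can be done in the wording before analysis. Whether other adverse events are adequately compared is a separate question and is not judged here.

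**What to change.** Keep both parts within primary outcome 3 and reword the outcome and the SAP.

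1. **Hypersensitivity reactions:** count them in all three groups over one common window that starts at first dose, with a stated end. Report counts by group and the A-B and A-C risk differences with 95% CI.
2. **Infusion-related reactions:** compare A with B only, per patient over the whole treatment course and labelled so. Report the risk difference with 95% CI. State that the outcome is not applicable to C.
3. **Interpretation:** state that the safety conclusion rests on these contrasts and their intervals, not on the three-group P-value.

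**Cost.** No extra patients are needed. The two reaction types must be recorded separately, with a rule for events that fit both. Group C needs hypersensitivity recorded from first dose. A window that runs to day 28 would need contact after discharge, while one that ends at discharge differs in length between patients. A versus B uses 159 patients and has low power (0.57 by Fisher for an assumed 10% v 2%), so the intervals will be wide and a non-significant difference must not be read as equal tolerability.

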## **Introduction:**

COVID-19 is an infectious viral disease caused by SARS CoV-2 (severe acute respiratory syndrome-corona virus 2) that has affected large number of people all over the world with high mortality rate (1). COVID-19 infection has been classified(2) as

1- Mild Illness: Individuals who have any of the various signs and symptoms of COVID-19 (e.g., fever, cough, sore throat, malaise, headache, muscle pain, nausea, vomiting, diarrhea, loss of taste and smell) but who do not have shortness of breath, dyspnea, or abnormal chest imaging.

2-Moderate Illness: Individuals who show evidence of lower respiratory disease during clinical assessment or imaging and who have an oxygen saturation ( $\text{SpO}_2$ )  $\geq 94\%$  on room air at sea level.

3-Severe Illness: Individuals who have  $\text{SpO}_2 < 94\%$  on room air at sea level, a ratio of arterial partial pressure of oxygen to fraction of inspired oxygen ( $\text{PaO}_2/\text{FiO}_2 < 300$  mm Hg, respiratory frequency  $> 30$  breaths/min, or lung infiltrates  $> 50\%$ ).

4-Critical Illness: Individuals who have respiratory failure, septic shock, and/or multiple organ dysfunctions.

Covid-19 pandemic stimulates research works to find a solution to this crisis from starting 2020 year up to now. With ending of 2021 year, various advances in pharmacotherapy against COVID-19 have emerged (3).

Regarding antiviral drugs used in treatment of COVID-19, remdesivir has approved by Food and drug administration (FDA)(4). Other drugs have shown controversial antiviral activity include: favipravir, ivermectin, nitazoxanide, hydroxychloroquine, ribavirin (5).

Recently, with the end of 2020, immunotherapy to target virus antigen has developed (6).Figure 1 shows two types of immunotherapy include active and passive immunotherapy. Active immunotherapy is to enhance body to produce antibodies against virus as by vaccination. Passive immunotherapy involves direct administration of prepared antibodies acting specifically against virus or administration of product containing antibodies like plasma (6).

In this study, the point of research is antibodies cocktail including REGN3048-3051(**casirivimab and imdevimab**). There are three targets for these antibodies to work as antiviral including:

- 1) antibodies that prevent the virus attachment and entry
  - 2) antibodies that inhibit the virus replication and transcription
  - 3) antibodies that hinder various steps of the immune system response

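### Secondary outcome 1, need for invasive mechanical ventilation, has no time window and no at-risk set, although patients already ventilated at day 0 are not excluded

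*Combined protocol and SAP*

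**What the plan says.** The Outcomes section gives the whole definition as "1-Need for invasive mechanical ventilation". The list stands under the line "Clinical outcomes measured before & during intervention", which does not separate status before treatment from status after it.

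On who can be enrolled, the Inclusion criteria admit "3-Moderate, sever or critical COVID-19 disease as defined by WHO". The Introduction describes the worst class as "4-Critical Illness: Individuals who have respiratory failure, septic shock, and/or multiple organ dysfunctions". The exclusion closest to this point is "4-patients expected to die within 48 hours"; none of the four exclusions mentions ventilation.

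On analysis, the SAP states "Intention-to-treat strategy will be used in this study". Its only sentence on secondary outcomes begins "While the secondary outcomes (hospital stay duration, icu stay duration and others) are compared using Kruskal-Wallis or ANOVA test", with the test chosen by data type and distribution. It names no subset for any outcome. Logistic regression is planned only if baseline differences are found, and only for the primary outcomes.

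The Sample Size section sets 53 patients for the antibody cocktail and 106 each for remdesivir and favipiravir. The Population section speaks of randomisation, while the Method section calls the study a non-RCT.

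**The concern.** A treatment can prevent intubation only in a patient who is not yet intubated. The plan lets patients who may already be ventilated into the study and gives no rule for handling them on this outcome. Under intention to treat with no subset named, they stay in the comparison, and there are two ways to score them:

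- as events, although the event came before treatment;
- as non-events, although they could not have had a new event.

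Either way they contribute no information on prevention, and they pull the observed risk difference towards zero. If the arms differ in the share ventilated at day 0, that difference passes into the result, and its direction depends on the scoring chosen. With allocation described as non-randomised and no adjustment planned for secondary outcomes, nothing in the SAP would remove it.

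**Working it through.** **Inputs from the documents.** Group sizes are 53, 106 and 106 (Sample Size; Table 2), and the significance level is 0.05 (SAP). No ventilation rate, effect size or power is given for this outcome. The one computed design figure, 246 patients, concerns 28-day mortality. It reproduces as a one-way ANOVA with three equal groups and effect size f = 0.2 (power 0.804 at 246 and 0.798 at 243), but it does not bear on ventilation.

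**Assumptions.** A share v of 10%, 20% or 30% is ventilated at day 0, equal across arms except in step 3. The risk p of new ventilation among the others is illustrative. Tests are two-sided at 5%.

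**Formulas.**
- Day 0 cases scored as events: observed risk = v + (1 − v)p.
- Day 0 cases scored as non-events: observed risk = (1 − v)p.
- In both, the risk difference is multiplied by (1 − v). The risk ratio moves towards 1 in the first case and is unchanged in the second when v is equal across arms.

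**Step 1: dilution, with new ventilation 30% (comparator) against 20% (cocktail); true ratio 0.67, true difference 10 points.**

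| v | Scored as events | Ratio | Scored as non-events | Ratio | Difference, either way |
|---|---|---|---|---|---|
| 10% | 37% v 28% | 0.76 | 27% v 18% | 0.67 | 9 points |
| 20% | 44% v 36% | 0.82 | 24% v 16% | 0.67 | 8 points |
| 30% | 51% v 44% | 0.86 | 21% v 14% | 0.67 | 7 points |

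For example, at v = 10%: 0.10 + 0.90 × 0.30 = 0.37; 0.10 + 0.90 × 0.20 = 0.28; 0.28/0.37 = 0.76.

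**Step 2: power, with new ventilation 35% against 15%, cocktail against one comparator (53 v 106), pooled-variance z test.** Power = Φ[(d − 1.96 s0)/s1]. Here d is the risk difference, s0 = √[p̄(1 − p̄)(1/n1 + 1/n2)] with p̄ the pooled risk, and s1 = √[p1(1 − p1)/n1 + p2(1 − p2)/n2]. The restricted analysis uses (1 − v) times each group size.

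Worked at v = 20%:
- Everyone, day 0 cases as events: risks are 48% v 32% and d = 0.16. Then p̄ = (53 × 0.32 + 106 × 0.48)/159 = 0.427, s0 = 0.0832 and s1 = 0.0804. So (0.16 − 0.1631)/0.0804 = −0.04, and power is 48%.
- Patients at risk only: 42.4 v 84.8 patients, d = 0.20, p̄ = 0.283, s0 = 0.0848 and s1 = 0.0754. So (0.20 − 0.1661)/0.0754 = 0.45, and power is 67%.

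| v | Everyone, as events | Everyone, as non-events | At risk only |
|---|---|---|---|
| 10% | 62% | 71% | 73% |
| 20% | 48% | 64% | 67% |
| 30% | 38% | 56% | 61% |

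With nobody ventilated at day 0, power is 78%.

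**Step 3: imbalance with no drug effect, new ventilation 30% in both arms.** Suppose 10% of the cocktail arm and 30% of a comparator are ventilated at day 0.
- As events: 0.10 + 0.90 × 0.30 = 37% against 0.30 + 0.70 × 0.30 = 51%. This is a false difference of 14 points, with about a 38% chance of p < 0.05 at 53 v 106.
- As non-events: 0.90 × 0.30 = 27% against 0.70 × 0.30 = 21%. This is a false difference of 6 points in the opposite direction.
- At risk only: 30% against 30%.

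**The case against.** The documents do not say that patients ventilated at day 0 are scored as events. The word need can fairly be read as need arising after enrolment. That stands, and a reader who infers that prevalent cases are certain to be counted as events goes further than the text. It does not dispose of the point: if only new need counts, intention to treat with no subset still leaves patients who cannot have the event in the denominator.

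The link from eligibility to ventilation is indirect. The Inclusion criteria rely on a WHO definition that is not reproduced, the Introduction takes its classes from a treatment guideline, and respiratory failure is not the same as intubation. Tube dosing of favipiravir ("orally or in Ryle tube / 12 hours") fits the presence of patients who cannot swallow but does not show ventilation. So the documents show that ventilated patients may be enrolled, not that they will be or how many.

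A reader might also infer that chance imbalance at day 0 could be as large as the effect sought. The documents do not support this. Their only stated effect is 20 points, for mortality, and chance imbalance is already allowed for in the test's type I error. The worry here is systematic imbalance, whose size is unknown. Nor does the SAP plan to pool the two comparators into a 53 v 212 contrast, so power on that basis would flatter either analysis.

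Finally, the WHO score and SOFA are recorded at day 0 and baseline characteristics are compared between groups. An imbalance could therefore be seen, but the plan gives no means of correcting for it on this outcome.

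**Conclusion.** The point holds as a gap in the outcome's definition that affects its analysis. Under either reading of need, the plan as written compares groups that may contain patients on whom treatment cannot act.

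The size depends wholly on the unknown share ventilated at day 0. For shares of 10% to 30%, counting these patients as events moves a true ratio of 0.67 to between 0.76 and 0.86. In the 35% against 15% example it costs 11 to 23 percentage points of power relative to the at-risk analysis (73 − 62; 61 − 38). Counting them as non-events costs much less, 2 to 5 points (73 − 71; 61 − 56), and leaves the ratio intact if the arms are balanced.

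These powers are for one pairwise comparison; the SAP plans a three-group test and states no contrast. They are for new ventilation alone. A reader should not infer that a composite with death would gain in the same way, since that was not calculated.

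This is one of eight secondary outcomes and does not touch the mortality comparison. It should be corrected because the result would be hard to interpret as written and the correction is cheap.

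**What to change.** In the Outcomes section, define secondary outcome 1 as new invasive mechanical ventilation after day 0 through day 28, among patients not invasively ventilated at day 0. In the SAP, name that set as the denominator. It is fixed by status before treatment, so patients are still compared in their assigned groups. Report the number ventilated at day 0 in each arm.

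Identify the set from the day 0 WHO score, which is already planned. The scale is not reproduced in the protocol, so confirm that the recorded category shows invasive ventilation explicitly.

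Death before ventilation competes with this outcome. Show new ventilation or death by day 28 in the same patients as a supporting analysis, with new ventilation alone remaining the defined outcome. The composite overlaps the primary mortality outcome and should be labelled accordingly.

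The cost is protocol and SAP wording and fewer patients in this one analysis. In the examples above, power for new ventilation is nonetheless higher than with everyone included. The restriction removes the distortion due to day 0 ventilation only. If allocation is not random, other differences in severity among the remaining patients can still confound the comparison.

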## **Sample Size:**

A total sample sizes of 246 patients would achieve at least 80 % power to detect a risk difference of 0.2 (20%) in the 28-day all-cause mortality (primary outcome) with a significance level ( $\alpha$ ) of 0.05 and 95% confidence level using the ANOVA or Kruskal-Wallis test of independent proportion in G\*Power software. To compensate for the estimated loss-to-follow-up and increase the study power, we will increase the sample size in both remdesivir and favipravir groups to be 106 patients compared to 53 patients in Antibodies cocktail Group As Antibodies cocktail product is available for only about 50 COVID-19 patients. In addition, the ratio (1:2:2) is the closest to reality according to number of patients who receive each drug.

The mortality data was estimated from the average mortality in August, September, and October 2021 at the Mansoura University Isolation Hospital among all hospitalized patients. Mortality rate is found to be about 360 cases in these 3 months (120 cases / month). The online system has been used to obtain mortality rate in these three months.

The current admission rate at the Mansoura University – Isolation Hospital is 250 cases per month on average; our needed sample is about 250 cases.

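### The invasive-ventilation outcome has no rule for death before ventilation, so by default an unventilated death counts the same as a recovery

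*Combined protocol and SAP*

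**What the plan says.** The Outcomes section lists eight secondary outcomes. The first is "Need for invasive mechanical ventilation", with nothing further: no definition of need as opposed to receipt, no time window, no at-risk population and no statement on patients who die. Death is a separate primary outcome, "28-days mortality rate (efficacy", and is not combined with ventilation anywhere.

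The Statistical Analysis Plan says that "Intention-to-treat strategy will be used in this study", that "Categorical variables will be presented as proportion and percent", and that "the secondary outcomes (hospital stay duration, icu stay duration and others) are compared using Kruskal-Wallis or ANOVA test". It names no composite, no competing-event method and no worst-rank rule for any secondary outcome.

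Two other places bear on the size of the problem. The Sample Size section reports, for the whole isolation hospital, "Mortality rate is found to be about 360 cases in these 3 months (120 cases / month", and an average of 250 admissions per month. The Exclusion criteria remove patients whose death is anticipated within 48 hours.

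**The concern.** Under intention to treat, a patient who dies stays in the denominator. On a yes/no ventilation item with no rule for death, someone who dies without being intubated takes the value no, and so does someone who walks out of hospital. The two values are equal although the outcomes are opposite.

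Death before intubation is a competing event, because it removes the chance to be ventilated. The trial's first aim is to evaluate an effect on 28-day mortality, and the sample size is set for a mortality difference of 0.2. A treatment effect on the competing event is therefore plausible, though not certain. If it occurs, an arm with more unventilated deaths will tend to show less ventilation, and an arm that keeps patients alive long enough to be intubated will tend to show more. The ventilation comparison could then point the opposite way from mortality for a reason unrelated to respiratory benefit.

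The gap concerns patients who are unventilated at entry. A rule for patients already ventilated at day 0 would not close it.

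**Working it through.** The plan gives no figure for the ventilation outcome. Its sample size of 246 concerns mortality, and this point does not depend on it.

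**Step 1: site mortality (Sample Size section).** 360 deaths / 3 months = 120 per month, as stated. 120 / 250 admissions = 0.48. This is crude hospital mortality. Deaths are from August to October 2021 and admissions are a current average, so the periods differ, and it is not 28-day mortality in eligible patients.

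**Step 2: patients affected.** Affected share = mortality × share of deaths that are unventilated. The second factor is not in the documents, so a range is assumed. The 28% column is 48% less the planned difference of 20 points.

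| Assumed unventilated share of deaths | At 48% mortality | Of 53 (group A) | Of 106 (B or C) | At 28% mortality |
|---|---|---|---|---|
| 10% | 0.48 × 0.10 = 4.8% | 2.5 | 5.1 | 2.8% |
| 30% | 0.48 × 0.30 = 14.4% | 7.6 | 15.3 | 8.4% |
| 50% | 0.48 × 0.50 = 24.0% | 12.7 | 25.4 | 14.0% |

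The 48-hour exclusion would lower these somewhat. The documents do not allow that to be quantified.

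**Step 3: can the direction reverse?** Take constant daily hazards, all assumed: intubation 0.02 and recovery 0.03 in both arms; death before intubation 0.01 in one arm and 0.02 in the other. With H the sum of the three hazards, the 28-day probability of each first event is (its hazard / H) × (1 − e^(−28H)).

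- Less lethal arm: H = 0.06 and 1 − e^(−1.68) = 0.8136. Ventilation = (0.02/0.06) × 0.8136 = 27.1%. Death without ventilation = (0.01/0.06) × 0.8136 = 13.6%. Either = 40.7%.
- More lethal arm: H = 0.07 and 1 − e^(−1.96) = 0.8591. Ventilation = (0.02/0.07) × 0.8591 = 24.5%. Death without ventilation = 24.5%. Either = 49.1%.

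The intubation hazard is the same in both arms, yet the more lethal arm shows 2.6 points less ventilation. Ventilation or death differs by 8.4 points in the other direction.

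**Step 4: would it be significant here?** With 53 patients in the more lethal arm and 106 in the other, the standard error of the ventilation difference is √(0.245 × 0.755/53 + 0.271 × 0.729/106) = 0.073. The difference is 0.026/0.073, or about 0.36 standard errors. The composite difference is 0.084/√(0.491 × 0.509/53 + 0.407 × 0.593/106) = 0.084/0.084, or about 1.0. Neither would be significant by itself.

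**Step 5: what the composite cannot show.** Assume 50% ventilated and 14.4% dying unventilated, so the composite is 64.4%. If 10 points of patients who would have been ventilated die first instead, ventilation falls to 40%, death without ventilation rises to 24.4%, and the composite is still 64.4%. If instead half the unventilated deaths become ventilations, ventilation rises to 50 + 7.2 = 57.2%, death without ventilation falls to 7.2%, and the composite is again 64.4%. Only the component table shows either change.

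**The case against.** The strongest reply is that 28-day mortality is the first primary outcome and is compared by group under intention to treat, so an excess of deaths would be visible beside the ventilation result. That stands, and it limits the priority. It does not close the gap: two separate marginal rates do not show which deaths were unventilated, so a reader cannot repair the ventilation figure from them.

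Second, the plan nowhere says that an unventilated death is a success. That is true. The scoring is inferred as the default for a yes/no item under intention to treat with no rule for death, and nothing in the documents prevents it.

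Third, the distortion is conditional. A reader might infer from the mortality aim that the ventilation result must be biased. The documents do not support this: they say nothing about where in the course of care deaths fall, and equal unventilated death in the arms gives no bias in direction from this source.

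Fourth, the sizes are largely assumed, and the 48-hour exclusion removes some of the deaths in question. Both are correct. Patients who die later, or unexpectedly early, remain.

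Fifth, a composite is not the only sound choice. A ventilation proportion over all patients is a legitimate cumulative incidence if deaths without ventilation are shown beside it. This is accepted in the fix.

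**Conclusion.** The gap is real. The ventilation outcome has no rule for death, and the default treats an unventilated death as equivalent to recovery. Under the assumed shares, about 5%, 14% or 24% of patients would be affected at 48% crude mortality, and somewhat fewer after the 48-hour exclusion. Bias in direction requires unventilated death to differ between arms. In the illustration, doubling the hazard of death before intubation moves ventilation from 27.1% to 24.5% while ventilation or death rises from 40.7% to 49.1%. All the hazards and the unventilated share are assumptions.

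Three stronger readings go too far. The protocol ranks none of its secondary outcomes, so this is not a key one. A statistically persuasive contradiction of the mortality result is unlikely at 53 versus 106 patients. And the composite does not by itself expose every distortion, because it is unchanged when patients only move between its components. For a secondary outcome reported beside primary mortality, the priority is minor to moderate.

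**What to change.** In the Outcomes section, replace secondary outcome 1 with invasive mechanical ventilation or death by day 28. In the Statistical Analysis Plan, state that this composite is the analysed outcome and that its two components, ventilation and death without ventilation, are always tabulated by arm. The table is essential, for the reason shown in step 5.

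An acceptable alternative is to keep ventilation as the outcome, estimated as a cumulative incidence with death as a competing event. The ventilation figures would still be those in step 3, so the cumulative incidence of death without ventilation must be shown beside them.

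The same SAP paragraph can set the rule for death in the other secondary outcomes.

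The cost is wording only. Ventilation and 28-day death are already outcomes, so no extra visits, tests or patients are needed. The downside is that the composite is less specific to ventilation and partly repeats the primary mortality outcome.
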